3.2 Study Endpoints

3.2.1 Primary Study Endpoints

The primary endpoints are feasibility (retention of participants with COPD) and acceptability (qualitative data, CATCH attendance rate, and % adherence to home breathing exercises) of the CATCH intervention.

3.2.2 Secondary Study Endpoints

The secondary endpoints are estimates of short-term treatment effects (at 10 weeks), which include: exercise capacity; DMQ-CAT dyspnea; 6MWD; SGRQ quality of life; exercise adherence; ETCO₂; RR; Borg Rate of Perceived Exertion (RPE); anxiety; CRQ Mastery; SEBQ dysfunctional breathing symptoms, moderate or vigorous physical activity (MVPA); and PROMIS-36 quality of life (physical function, anxiety, depression, satisfaction with participation in social roles, sleep disturbance, and fatigue).

4 Study Enrollment and Withdrawal

4.1 Inclusion Criteria

To be eligible to participate in this study, an individual must meet all of the following criteria:

CONFIDENTIAL

This material is the property of the NYU School of Medicine and Langone Medical Center. Do not disclose or use except as authorized in writing by the study sponsor Behavioral Intervention Template Version: 5 MAY 2017

(1) is over 40 years of age; (2) has COPD documented in their electronic medical record, as defined by FEV₁/FVC of < 0.70 on pulmonary function testing (spirometry), or as shown on a chest CT; (3) can maintain oxygen saturation (SaO₂) ≥ 90% on room air at rest; (4) is medically cleared to participate in NYULMC's outpatient pulmonary rehabilitation program; and (5) is English speaking. Pregnant patients will not be enrolled in the study.

4.2 Exclusion Criteria

An individual who meets any of the following criteria will be excluded from participation in this study:

(1) requires 24-hour supplemental oxygen; (2) has cognitive impairment as measured by ≤23/30 on the Mini Mental State Examination (MMSE)⁷⁷; (3) is actively being treated for lung cancer (E.g. with chemotherapy or upcoming surgery); (4) has morbid obesity (BMI > 40); (5) is currently smoking; and (6) has unstable cardiac disease defined by a history of a myocardial infarction in the past 3 months.

4.3 Vulnerable Subjects

Vulnerable subjects will not be recruited in this study.

4.4 Strategies for Recruitment and Retention

Active recruitment efforts to ensure the inclusion of appropriate numbers of patients from each sex, racial, and ethnic group will include: 1) a paper recruitment flyer distributed to potential subjects by the study team within Rusk Rehabilitation; 2) recruitment after pulmonary rehabilitation consultation by [name]; and 3) use of an automated EHR alert system.

To increase retention of subjects, the research assistant will send visit reminders via the subject's preferred method of contact (phone, text, or email) 24 hours prior to all scheduled visits. Participants will also receive compensation for their time which will be pro-rated should they not complete the entire study. If retention rates drop below acceptable levels, the study team will engage CTSI Recruitment and Retention Unit (CTSI RRU) for consultation on engagement strategies and methods to improve retention.

4.4.1 Use of DataCore/Epic Information for Recruitment Purposes

This study will utilize EPIC to alert the study team of potentially eligible subjects. We will use an EHR report system. The pulmonary rehabilitation intake evaluation schedule in EPIC will also be used to alert the study team of potential participants.

Any recruitment information sent by email will utilize Send Safe email.

Once potential subjects have been identified, the study team will notify the treating physician (TP) that they have patients eligible to participate as follow:

- TP has been notified that the study team will contact potential subjects directly, by letter, phone, and/or email.

Once contact is made, approved recruitment language using a script will be used to communicate the reason they are being contacted and subjects will be asked if they are interested in participating in this specific study. Should the potential subjects agree, the study team will provide the subjects with information regarding the next steps for participation.

If a subject requests information regarding opting out of further recruitment for all research, subjects will be directed to contact [contact] or [name].

CONFIDENTIAL

This material is the property of the NYU School of Medicine and Langone Medical Center. Do not disclose or use except as authorized in writing by the study sponsor Behavioral Intervention Template Version: 5 MAY 2017

4.5 Duration of Study Participation

The duration of study participation is approximately 10 - 12 weeks including: 1 – 2 weeks for screening and recruitment, and a 10-week intervention phase. There is no follow-up period.

4.6 Total Number of Participants and Sites

Recruitment will end when approximately 40 participants are enrolled at Rusk Rehabilitation for this single-site study. It is expected that approximately 40 participants will be enrolled to produce 22 evaluable participants due to drop-outs.

4.7 Participant Withdrawal or Termination

4.7.1 Reasons for Withdrawal or Termination

Participants are free to withdraw from participation in the study at any time upon request. An investigator may terminate participation in the study if:

- Any clinical adverse event (AE) or other medical condition or situation occurs such that continued participation in the study would not be in the best interest of the participant
- The participant meets an exclusion criterion (either newly developed or not previously recognized) that precludes further study participation
- Participant requires hospitalization for an exacerbation and is unable to resume their PR program within 2 weeks following an exacerbation.

5 Behavioral/Social Intervention

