1.1 Background Information and Relevant Literature

About 14% of Americans have Chronic obstructive pulmonary disease (COPD) and it is the third leading cause of death in both the U.S.A. and the world.^{1,2} The prevalence and burden of COPD on patients, their families, and society is high and will only continue to grow with the aging of the population.³⁻⁶ COPD is characterized by progressively declining ventilatory function,^{7,8} increased dyspnea, chronic inflammation, and increased sympathetic nerve activity⁹. Dyspnea (labored, uncomfortable breathing¹⁰) is the most prevalent, emotionally distressing, and disabling symptom of COPD; it limits physical activity, exercise tolerance, and quality of life and is associated with increased mortality.¹¹⁻¹³ It consists of several qualitatively distinct sensations, such as “air hunger”, increased “urge to breathe”, “chest tightness”, and feeling “starved for air”.¹⁴ It is the main reason why patients with COPD seek medical and rehabilitation services. The insula, a sensorimotor area of the limbic system in the brain, activated during inspiration, plays an integral role in dyspnea perception by acting as an alarm center.¹⁴⁻¹⁶ The high prevalence of comorbid anxiety disorders (up to approximately 40%) and panic disorder (up to 10 times higher than in the general population) in COPD^{17,18,19} increases the severity of dyspnea and related disability,²⁰⁻²² and increases the risk for acute COPD exacerbations (ACOPDE) and associated hospitalizations²³.

In COPD, dyspnea is associated with a vicious cycle of physical activity (PA) decline and deconditioning, leading to increased ventilatory requirements of PA, further impairment of physical function and quality of life (QOL), and social isolation;^{24,25} creating a disability spiral²⁶. Dyspnea and associated anxiety also contribute to a vicious circle of abnormally rapid breathing (tachypnea), air trapping, and lung hyperinflation both at rest and with physical exertion (dynamic hyperinflation), leading to further dyspnea and PA limitations and impaired QOL (see Appendix A for the COPD model underlying this study).²⁴ Anxiety and increased sympathetic nervous system arousal can impair the function of the diaphragm, the most important muscle of breathing; causing it to shorten, lower, and flatten (inspiratory position) and become hypertonic; limiting its functions such as venous and lymphatic return and optimal posture.^{27,28}

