PLB training (quiet breathing in through the nose and out through pursed lips with expiration twice as long as inspiration) decreased respiratory rate in adults with COPD,^{61,62} alleviated long-term dyspnea compared with control groups⁴⁶, and improved oxygen saturation⁶². By improving expiration, PLB reduced dynamic hyperinflation during daily activities and submaximal exercise in some patients with COPD.^{62,63} Similarly, Visser⁶⁴, found that PLB decreased hyperinflation and oxygen saturation, and decreased ETCO₂, and RR in patients with severe COPD. PLB has been endorsed in evidence-based practice guidelines to relieve dyspnea in advanced COPD.^{11,65} A systematic review of PLB for stable COPD found that PLB (1) reduced RR and increased tidal volume both at rest and during sub-maximal exercise, and (2) improved oxygen saturation.⁶⁶

Slow-breathing exercises, such as PLB, are often provided as part of a multicomponent rehabilitation intervention or adjunctive modality to potentially boost the effectiveness of exercise training or behavioral therapy, however more research is needed.^{40,67,68} A randomized study found that health coaching (consisting of daily slow breathing exercises, physical exercises, and an emergency plan combined with motivational interviewing) reduced short-term rehospitalizations and improved health-related quality of life in adults with COPD compared with usual care.⁶⁹

Slow, controlled breathing exercises (with prolonged expiration) reduce anxiety and sympathetic nerve activity. For example, slow breathing (6 breaths per minute; 3s inspiration and 7s exhalation) reduced sympathetic nerve activity compared with 15 breaths per minute and spontaneous breathing and improved baroreflex sensitivity in patients with COPD.⁹ Similarly, Buteyko-device-guided breathing training using capnometry reduced panic symptoms, panic-related cognitions, and perceived control, and increased PCO₂ to normocapnic levels in adults with panic disorder and agoraphobia.⁷⁰

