Attachment A
Schedule of Events

Activity	EHR PreScreening	Pre- Screening Call	Baseline (Week 0)	Treatment Visits (Weeks 0 – 6 ±2)	Post- Treatment Phone Interview (Week 7 ±2)	PR Discharge Evaluation (Week 10 ±2)
Study team procedures						
Informed Consent		X	X			
Screening						
Age	X		X			
Mini Mental State Examination (MMSE)			X			
Pulmonary Rehabilitation Clearance	X		X			
English Proficiency		X	X			
Pulmonary Function Testing or Chest CT results	X		X			
Medical History (active treatment for lung cancer, supplemental oxygen prescription, cognitive impairment or dementia, unstable cardiac disease / myocardial infarction < 3 months)	X		X			
Body Mass Index	X		X			
Current Smoking Status	X	X	X			
Baseline Assessment						
Modified Medical Research Council Questionnaire (mMRC) ¹⁰⁹			X			
Demographics / Social Economic Status			X			
Lung Function			X			

Smoking History			X			
Pulmonary Diagnoses and Comorbidities			X			
COPD Exacerbation History			X			
Primary Outcome: Feasibility						
Retention of participants: # of drop-outs and # of participants lost to follow-up						X
Primary Outcome: Acceptability (CATCH participants only)						
Semi-structured interviews					X	
% of CATCH intervention sessions attended				X		
Adherence to Breathing Home Exercises – Daily Breathing Log and Address Stress app				X		

CONFIDENTIAL

This material is the property of the NYU School of Medicine and Langone Medical Center. Do not disclose or use except as authorized in writing by the study sponsor
 Drug/Device Template Version: 13 JUN 2016

Study number: s17-01672

Page 2

Version: 6/9/2018

Activity	EHR PreScreening	Pre-Screening Call	Baseline (Week 0)	Treatment Visits (Weeks 0 – 6 ±2)	Post-Treatment Phone Interview (Week 7 ±2)	PR Discharge Evaluation (Week 10 ±2)
Secondary Outcomes						
Cardiopulmonary Exercise Stress Test (CPET) – standard of care			X			X
6-Minute Walk Test & Borg RPE – standard of care			X			X
DMQ-CAT			X			X
St. George's Respiratory Questionnaire			X			X
Generalized Anxiety Disorder (GAD-7)			X			X
End-tidal Carbon Dioxide (ETCO2)			X			X

Respiratory Rate (RR)			X			X
CRQ-Mastery			X			X
Self-Evaluation of Breathing Questionnaire (SEBQ)			X			X
PROMIS-36 SF			X			X
Physical Activity (MVPA)			X			X
Adherence to Pulmonary Rehabilitation Exercise Training Sessions						X
Health Questionnaire						X

CONFIDENTIAL

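### Section 4.7.1 allows study participation, not just treatment, to be ended after a serious exacerbation or a new exclusion criterion, with no Week 10 outcomes sought afterwards

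*Combined protocol and SAP*

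**What the plan says.** Section 4.7.1 introduces its grounds with "An investigator may terminate participation in the study if". One ground is an adverse event or other situation that makes continuing contrary to the participant's interest. The two at issue here are "The participant meets an exclusion criterion (either newly developed or not previously recognized) that precludes further study participation" and "Participant requires hospitalization for an exacerbation and is unable to resume their PR program within 2 weeks following an exacerbation". Section 4.2 lists "requires 24-hour supplemental oxygen" and a myocardial infarction in the previous three months among the exclusion criteria. Section 4.7.1 does not separate stopping CATCH or PR from leaving the study.

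The rest of the plan does not bring these participants back:

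- Section 4.5: "There is no follow-up period".
- Section 7.1 records events past the last day of participation (7 days for non-serious AEs, 30 for SAEs), but no outcomes.
- Attachment A schedules the clinical and questionnaire outcomes at baseline and at the PR discharge evaluation (Week 10 ±2), with nothing between.
- Section 8 specifies ANCOVA on change scores and paired t-tests. It names no analysis population and no missing-data method.
- Retention is a primary endpoint (Section 3.2.1). Attachment A describes it as "Retention of participants: # of drop-outs and # of participants lost to follow-up". Neither term is defined, and investigator termination has no line of its own.
- Only the clinician running the exercise stress tests is stated to be blinded (Section 3.1). The PI delivers CATCH (Section 5.1).

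**The concern.** The events that can trigger termination occur after randomisation and follow the patient's course. The protocol also gives reason to think that they might depend on treatment. Section 1.1 says that comorbid anxiety, which CATCH aims to reduce, "increases the risk for acute COPD exacerbations (ACOPDE) and associated hospitalizations". Section 1.2 cites a coaching package with slow breathing as one component that "reduced short-term rehospitalizations and improved health-related quality of life in adults with COPD compared with usual care". This is plausibility, not evidence that CATCH changes exacerbations within 10 weeks.

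The exacerbation ground depends on resuming PR, not on CATCH. CATCH is six weekly sessions, while PR runs for 10 weeks. A participant could attend all six sessions, be admitted in week 7, and lose every Week 10 outcome.

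Two things are at stake. First, this pilot is meant to supply mean changes and variances for a larger trial; they could come from a group from which poor courses have been removed by a discretionary decision that may be made with the arm known. Second, Section 4.4 answers low retention with advice on engagement. That does not address hospitalisation, so the two kinds of loss need to be told apart.

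**Working it through.** **1. The plan's own figures.** Section 8: 22 patients, 2:1, difference 1.25 SD, two-sided 0.05, about 80% power. Normal approximation with n₁ = 14.67 and n₂ = 7.33: √(n₁n₂/22) = √4.889 = 2.211; 1.25 × 2.211 = 2.764; Φ(2.764 − 1.96) = Φ(0.804) = 78.9%. The stated figure reproduces. (The noncentral t gives 74.8%.) The standard error of the difference at 15 versus 7 is √(1/15 + 1/7) = 0.46 SD.

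Section 4.6 expects 40 enrolled to yield 22 evaluable, a loss of 18/40 = 45%. The Protocol Summary gives 26 evaluable, a loss of 14/40 = 35%. These need reconciling. Neither document section gives a rate of exacerbation, hospitalisation or termination, so what follows uses an assumed range.

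**2. How a participant leaves the analysis.** Termination (4.7.1) ends participation; no outcome visit follows (4.5, Attachment A); without a Week 10 value there is no change score; without a change score there is no contribution to the ANCOVA or paired t-test (Section 8).

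**3. Shift within one arm.** Assume normally distributed changes, scored so that higher is better, and that the share q lost is exactly the worst q. For a given q this is the largest possible shift. The mean of those kept exceeds the mean of all by φ(z_q)/(1 − q), in SDs of change.

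| q lost | φ(z_q) | shift (SD) |
|---|---|---|
| 5% | 0.103 | 0.103/0.95 = 0.11 |
| 10% | 0.175 | 0.1755/0.90 = 0.19 |
| 15% | 0.233 | 0.233/0.85 = 0.27 |

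**4. Shift between arms.** Bias = shift(CATCH) − shift(control); positive flatters CATCH.

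- Equal loss, same selection: 0.
- 5% CATCH, 10% control: 0.109 − 0.195 = −0.09. Reversed: +0.09.
- 5% CATCH, 15% control: 0.109 − 0.274 = −0.17. Reversed: +0.17.
- 10% in both arms, but the worst courses in one and a random 10% in the other: ±0.19, because random loss shifts nothing.

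Equal counts are not equal loss under 2:1 allocation. If all 40 are randomised (about 27 and 13), two terminations per arm are 2/27 = 7.4% versus 2/13 = 15.4%.

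**5. Retention.** Each participant moves it by 1/40 = 2.5 points. If 5%, 10% or 15% of the 40 were terminated under these grounds, that is 2, 4 or 6 people, or 11%, 22% or 33% of the 18 expected losses. Had they been assessed at Week 10, retention would be 24/40 = 60%, 26/40 = 65% or 28/40 = 70%, against 22/40 = 55%.

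**The case against.** The strongest reply is that the rule is narrow and discretionary. It says that the investigator may terminate. It covers only hospitalised exacerbations without timely return to PR, and only exclusion criteria that preclude continuing. Some exclusion criteria, such as current smoking, are not the natural course of COPD. All of this stands: the rule permits removal and does not impose it. Discretion does not remove the problem, though, because the decision can be made with the arm known.

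A reader might infer that harm, or a benefit on exacerbations, is hidden. The documents do not support that. Hospitalisation is an SAE (Section 7.2.2), AEs are recorded whatever their cause (Section 7.4), SAE capture runs 30 days past participation (Section 7.1), and Section 6.1.1 says that withdrawals associated with adverse events will be monitored. What goes unmeasured is the effect on Week 10 scores.

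A reader might also infer that the treatment comparison is biased in a known direction, or that the drop-out count is inflated. The first needs loss, or outcomes among the lost, to differ by arm, and nothing in the documents says that they will. The second is an inference, because drop-out is undefined; for feasibility of a larger trial, disease-related loss is real loss. Tolerability is also covered by the acceptability endpoints (interviews, attendance, home adherence).

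Finally, the illustrated biases are well below the 0.46 SD standard error, in analyses that Section 8 calls preliminary, and the missing analysis population and missing-data method are a wider gap. Both points stand, and they limit this to an inexpensive improvement.

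**Conclusion.** The point holds in a limited form. As written, Section 4.7.1 merges stopping treatment with leaving the study, and no part of the plan recovers Week 10 outcomes. Poor courses can therefore drop out of the 10-week analysis.

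Under the assumed 5–15% loss of the worst courses, each arm's mean change would look about 0.11–0.27 SD too good. Between arms, the bias is 0 with equal loss and the same selection, and about ±0.09 to ±0.17 SD at 5% versus 10% or 15%. These figures rest on normal changes and on the lost being exactly the worst. The documents fix neither the sign nor the size. The effect on retention depends on a definition that the plan does not give.

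**What to change.** Leave the clinical decision on CATCH and PR with the investigator, as now, and add to Section 4.7.1 a sentence such as: *Participants whose CATCH or PR is stopped remain in the study for the Week 10 assessment unless they withdraw consent.* At minimum, collect the existing questionnaires (DMQ-CAT, SGRQ, GAD-7, CRQ-Mastery, SEBQ, PROMIS-36, physical activity), by phone if needed, with CPET and 6MWT only if clinically permitted. State in Section 8 that these data enter the between-group analysis as randomised. In Attachment A, report retention with investigator- or disease-driven stopping shown separately from participant withdrawal and loss to follow-up.

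The cost is a short paragraph, a few extra phone contacts and slightly noisier estimates. Some exercise tests will still be missing, so Section 8 still needs a stated approach to missing data.

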5.1 Study Behavioral or Social Intervention(s) Description

Capnometry-Assisted Training for COPD to Slow the Breath (CATCH) Intervention.

The CATCH intervention was developed to promote a slower, more regular, efficient breathing pattern and optimum breathing amplitude and mechanics, including improved respiratory muscle function (especially of the diaphragm), reduced dyspnea, improved autonomic nervous system regulation, and neural modulation (creating new neural connections).^{15,28,78} A portable capnometer (CapnoTrainer, Better Physiology, Cheyenne, WY) will be used in-session to provide continuous visual feedback of RR, ETCO₂, rhythm, and depth of breathing, and ratio of inspirations to expirations. The CapnoTrainer is not FDA approved. We will be using the CapnoTrainer device under a non-significant risk device determination. Hard copy print outs from each capnometry session will be made and reviewed with patients to discuss progress.

The tailored CATCH intervention will emphasize a slow, quiet, regular, nasal breathing pattern, as well as PLB in facilitatory supine and forward leaning postures.⁷⁹ Patients will be educated to regulate the volume of their breathing, use a ratio of 40% inhalation to 60% exhalation (with breath pauses), and approximately 10 – 12 breaths per minute at rest, facilitated by a manual evaluation of respiratory pattern.^{27,80,81} Chest and mouth breathing will be discouraged (because they contribute to dyspnea and can trigger bronchoconstriction and airway hyperreactivity), as will breath sounds (such as sighing), deep and rapid breathing (hyperpnea), paradoxical breathing (drawing in of the abdomen during inspiration and expansion during expiration), and forceful, irregular breathing.⁸²⁻⁸⁴ Patients will also be directed to breathe mindfully (“paying attention on purpose, in the present moment, nonjudgmentally”^{85, p.91}).^{41,48,56} CATCH will be once weekly for 6 weeks, for a total of 6 sessions; each session will be approximately 60 minutes duration. The principal investigator will implement the CATCH intervention.

Some breathing exercises during CATCH sessions will be audio or video recorded or photographed to provide participants with additional instructions to use at home to help them complete guided home breathing exercises. For the at-home training, patients will also use the Address Stress app on a smartphone or computer tablet for tailored paced breathing exercises. The breathing app will provide auditory and visual cues for the paced exercises. Patients will also keep a breathing exercise log of total

CONFIDENTIAL

This material is the property of the NYU School of Medicine and Langone Medical Center. Do not disclose or use except as authorized in writing by the study sponsor Behavioral Intervention Template Version: 5 MAY 2017

daily minutes completed. Patients will also be instructed in upper body stretching exercises to perform daily as part of their home exercises.⁸⁶ The Address Stress app collects email address for downloading the app on a personal smartphone or tablet computer. The app transmits adherence data only via email to the study PI. It is not necessary for participants to own a smartphone or tablet computer to use the app since tablet computers will be loaned to participants as needed to access the app.

CATCH will be grounded in social cognitive theory⁸⁷ to promote behavior change, improve selfefficacy and outcome expectation, and support the use of interactive technologies to guide and motivate patients. CATCH also applies the hyperventilation model, in which hyperventilation leads to hypocapnia, dyspnea, and panic.⁸⁸ Other underlying theoretical models are the neurophysiological model of dyspnea,³¹ the model of mindfulness⁴⁸, and the neurophysiological theory of functional connectivity in COPD.¹⁵

Pulmonary Rehabilitation (PR).

Patients in both treatment groups will participate in a 10-week (16 - 20 sessions) comprehensive PR program. As per standard of care, the control group will receive the 10-week PR program with traditional breathing training instruction only (without biofeedback). The PR program comprises two or three exercise training sessions per week implemented by physical therapists (each of 1-hour duration). PR sessions include individualized self-management education.

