1.2 Rationale

Hypotheses

1. Participants' change scores in the CATCH group will be significantly greater compared with those of the control group for the primary outcomes of peak HR, exercise duration, 6MWD, DMQ-CAT dyspnea, SGRQ quality of life, and exercise adherence (> % of sessions or < time to complete).
2. Ve will decrease (indicating decreased RR and improved breathing efficiency) and peak VO₂ will increase in the CATCH group (indicating improved pulmonary function) and changes will be significantly greater compared with the control group.
3. Participants' change scores in the CATCH group will be significantly greater compared with the control group for the secondary outcomes of RR, ETCO₂, Borg RPE, anxiety, CRQMaster, SEBQ, PROMIS-36, and Physical Activity.

CONFIDENTIAL

This material is the property of the NYU School of Medicine and Langone Medical Center. Do not disclose or use except as authorized in writing by the study sponsor Behavioral Intervention Template Version: 5 MAY 2017

Justification for hypotheses

Our hypotheses for the primary outcomes of Ve, peak VO₂, and exercise time are consistent with findings and trends from a previous COPD trial of device-guided respiratory training combined with PR.⁴³ By allowing more time to effectively empty the lungs during prolonged exhalation, a slow breathing pattern can improve breathing efficiency, reduce lung hyperinflation, improve diaphragmatic mobility and chest wall mechanics, resulting in less dyspnea, improved exercise capacity and tolerance, eucapnia (optimal carbon dioxide pressure), and the prevention of neuromechanical uncoupling.^{8,59,24,29} In a meta-analysis of four studies of mostly severe COPD, slow breathing exercises (PLB, DB, and 3-months of yoga) improved 6MWD by 35 - 50 meters, which was beyond the minimal important difference^{47,44}.

Device-guided slow breathing training when combined with PR using a pneumotachometer interfaced with a computer display of respiratory and goal feedback reduced dynamic hyperinflation and improved breathing pattern (increased expiratory time) in COPD compared with both PR-alone and breathing-training-alone groups.⁴³ Device-guided breathing instruction in COPD also improved self-efficacy (breathing confidence) compared with a traditional method of teaching pursed lips breathing (PLB).⁶⁰

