5.1.2 Assessment of Subject Compliance with Study Intervention

Pulmonary rehabilitation session attendance documented in the EMR will be used to evaluate PR adherence. Adherence to breathing exercises for participants in the CATCH intervention will be evaluated using a paper breathing log. Adherence data will also be available from the AddressStress app.

6 Study Procedures and Schedule

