6.1.1 Study Specific Procedures

See Schedule of Events – Attachment A for description of study specific procedures.

Figure 2. CATCH Scheduling of Tests.

CONFIDENTIAL

This material is the property of the NYU School of Medicine and Langone Medical Center. Do not disclose or use except as authorized in writing by the study sponsor Behavioral Intervention Template Version: 5 MAY 2017

Outcome Measures.

Exercise Capacity: Clinical treadmill stress tests will be used to measure exercise capacity pre- and post-treatment, including: peak VO_2 (ml/kg/min and % predicted based on age), Ve (l/min) at isotime (2-minutes prior to exercise termination at baseline), peak HR, and exercise duration. Exercise stress tests will be administered by a clinician as part of standard care.

Six Minute Walk Test (6MWT). The 6MWT is a standardized, performance-based test to measure exercise tolerance (functional status) using the American Thoracic Society's standardized protocol.⁸⁹ Clinicians will administer the 6MWTs as part of standard care.

Dyspnea Management Questionnaire Computer Adaptive Test (DMQ-CAT)⁹⁰. The DMQ-CAT is a COPD-specific functional status measure that captures four dyspnea domains: intensity, anxiety, activity avoidance, and self-efficacy. Higher scores are better. It has been shown to be reliable and valid in rehabilitation and primary care patients.^{91,92} The DMQ-CAT uses computer adaptive testing to tailor dyspnea items and administer up to 20 items.

St. George's Respiratory Questionnaire (SGRQ).^{93,94} The SGRQ is a widely used quality of life measure for adults with chronic airflow limitation, consisting of three domains: symptoms, activity, and impacts. Lower scores indicate better quality of life. The SGRQ activity domain measures dyspnea and its functional impact. The symptoms and impacts domains measure several respiratory symptoms and psychosocial functioning respectively. Several studies have supported its reliability and validity.^{93,95,96} We will use the American version for this study.⁹⁴

Adherence to Exercise Training. Exercise adherence is the % of exercise training sessions completed and the time taken (in weeks) to complete the PR program. Adherence to daily home breathing exercises is the % completed (at least 5 minutes per day for 6 weeks; the goal is 70% adherence).

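### Raw weeks to complete PR, one of two measures of the secondary exercise adherence endpoint, mixes planned schedule with adherence, and three PR sessions per week does not fit the stated programme

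*Combined protocol and SAP*

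**What the plan says.** Section 5.1 describes PR for both arms in two statements: "Patients in both treatment groups will participate in a 10-week (16 - 20 sessions) comprehensive PR program", and then "The PR program comprises two or three exercise training sessions per week". It does not say who trains twice and who three times a week, how a participant's session total is set within 16 to 20, or whether missed sessions are made up.

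Section 6.1.1 defines the outcome: "Exercise adherence is the % of exercise training sessions completed and the time taken (in weeks) to complete the PR program". Hypothesis 1 in Section 1.2 gives the favourable direction: "exercise adherence (> % of sessions or < time to complete". A shorter time therefore counts as better adherence.

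Section 3.2.2 places the outcome among the secondary endpoints ("DMQ-CAT dyspnea; 6MWD; SGRQ quality of life; exercise adherence"), and Attachment A does the same. Section 5.1.2 names the data source: "Pulmonary rehabilitation session attendance documented in the EMR will be used to evaluate PR adherence". Attachment A sets the PR discharge evaluation at week 10, plus or minus 2 weeks. The ANCOVA covariates in Section 8 are age, FEV1 and mMRC; planned PR schedule is not among them.

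**The concern.** The programme length, session count and weekly frequency in Section 5.1 cannot all hold for someone who trains three times a week throughout. On its own that is a wording problem. It reaches the analysis because the time a participant takes to finish PR is scored as adherence.

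Weeks to complete depends on three things: how many sessions were planned, how many were planned per week, and how reliably the participant came. Only the third is adherence. If the first two vary between participants and are not recorded or scaled out, a difference in weeks cannot be read as a difference in adherence, and the measure can put participants in the wrong order. At stake is the meaning of one of the two exercise adherence measures, in a pilot meant to prepare for a larger study.

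**Working it through.** **Inputs.** From Section 5.1: 10 weeks, 16 to 20 sessions, 2 or 3 sessions per week. From Attachment A: discharge evaluation at week 10 ± 2, so from week 8. Assumed, because the documents are silent: each participant keeps one weekly frequency throughout, and, where stated, missed sessions are made up.

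**Step 1. Reproduce the stated count.** Sessions = frequency × weeks.
- Two per week: 2 × 8 = 16 and 2 × 10 = 20. The stated range is reproduced.
- Three per week: 3 × 10 = 30, and 3 × 8 = 24 even over 8 weeks. The stated range is not reproduced.

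**Step 2. Weeks to complete at full attendance.** Weeks = sessions / frequency. The last column takes three-per-week completion as no earlier than week 8.

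| Planned sessions | Two per week | Three per week | Gap | Gap if completion is not before week 8 |
|---|---|---|---|---|
| 16 | 8.0 | 5.3 | 2.7 | 8 − 8 = 0 |
| 18 | 9.0 | 6.0 | 3.0 | 9 − 8 = 1 |
| 20 | 10.0 | 6.7 | 3.3 | 10 − 8 = 2 |

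The two-per-week column alone shows a schedule effect: perfect adherence scores 8 or 10 weeks according to planned count.

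**Step 3. Can the ranking reverse? (missed sessions made up)** Weeks = sessions / (frequency × attendance).
- 18 sessions, three per week, 75% attendance: 18 / (3 × 0.75) = 8 weeks.
- 18 sessions, two per week, full attendance: 18 / 2 = 9 weeks.
- The less adherent participant finishes first. Break-even at equal counts: N / (3a) = N / 2, so a = 2/3 = 67%.
- If the faster 18-session schedule is instead paced to take 8 weeks at full attendance, break-even is 8 / 9 = 89%.
- With everyone on two per week, a 16-session participant against a fully attended 20: 16 / (2a) = 20 / 2, so a = 80%.

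**Step 4. If missed sessions are not made up.** The same two participants finish at 18 / 3 = 6 and 18 / 2 = 9 weeks whatever their attendance. Raw weeks then carries no adherence information.

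**Step 5. The percentage measure.** Sixteen sessions attended is 16 / 16 = 100% or 16 / 20 = 80%, depending on the planned count. This measure also needs a prescribed denominator.

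**Step 6. Test the replacement, weeks taken / weeks planned.**
- Made up: 8 / 6 = 1.33 against 9 / 9 = 1.0. Both complete 100%, and the ratio separates them.
- Not made up: 6 / 6 = 1.0 against 9 / 9 = 1.0, with 75% against 100% completed. The percentage separates them.
- Three per week, no missed sessions, 2-week medical pause: (6 + 2) / 6 = 1.33, the same as the 75% attender. With the pause excluded: (8 − 2) / 6 = 1.0. The ratio needs that exclusion.

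**The case against.** The strongest reply is that Section 5.1 never says a participant is fixed at two or at three sessions a week. Some weeks may have two and others three: four weeks of each gives 8 + 12 = 20 sessions in 8 weeks, which fits the count and the discharge window. A third session might be optional, in which case a faster finish would partly reflect uptake, as Hypothesis 1 intends. This stands as far as it goes: the two-schedule examples are conditional. It does not remove the point, because a planned count of 16 or 20 still moves full-adherence time between 8 and 10 weeks.

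Second, the ten weeks may be nominal. That resolves the mismatch in wording, but makes completion time openly dependent on schedule. Reading 16 to 20 as attended rather than planned sessions would imply 16 / 30 = 53% to 20 / 30 = 67% attendance at three per week, which the text does not say.

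Third, Attachment A opens the discharge evaluation at week 8. It governs the evaluation and is not a completion rule, but it is the only dated end to PR. If completion is no earlier than that, the between-frequency gap falls to 0 to 2 weeks. This stands and limits the size.

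A reader might cite Section 4.7.1, which lets the investigator end participation for someone hospitalised and "unable to resume their PR program within 2 weeks following an exacerbation", as proof that the measure rewards poor adherence, since a faster schedule absorbs a pause. It does not show that. A medical pause is not non-adherence; it shows only that pauses need separate handling.

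**Conclusion.** The point holds and is minor. Certain from the text: three sessions per week throughout does not fit 16 to 20 sessions in 10 weeks, and raw weeks is scored as adherence with no scaling to planned count or frequency. At two per week the planned count alone accounts for up to 10 − 8 = 2 weeks. Conditional on some participants being scheduled three times a week throughout, the gap at equal counts is up to 2.7 to 3.3 weeks, or 0 to 2 weeks if PR ends no earlier than week 8. Conditional also on missed sessions being made up, participants can be misranked.

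Three stronger readings are tempting and not supported:
- **That the arm comparison is biased.** Nothing says that schedule differs by arm. Equally, freedom from bias holds only if schedule is set independently of arm, and the documents do not say when or how it is set.
- **That the loss of precision is large.** The documents give neither the share on each schedule nor an SD for weeks to complete, so the added noise cannot be sized.
- **That a primary endpoint is affected.** Hypothesis 1 lists exercise adherence among primary outcomes, but Section 3.2.1 states: "The primary endpoints are feasibility (retention of participants with COPD) and acceptability". Retention and acceptability do not use this measure.

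What remains is poor interpretability and some noise in half of one secondary endpoint.

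**What to change.** - **Section 5.1:** reconcile frequency, session count and duration. Record each participant's prescribed sessions and prescribed weekly frequency at PR intake, before randomisation where possible, so that the planned schedule cannot depend on arm.
- **Section 6.1.1 and Hypothesis 1:** replace raw weeks with weeks taken, excluding documented medical pauses, divided by weeks planned, where weeks planned = prescribed sessions / prescribed weekly frequency. A value of 1.0 means on schedule.
- **Percent completed:** use prescribed sessions as the denominator. Keep both measures, since each works where the other does not.

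The cost is wording in Sections 1.2, 5.1 and 6.1.1, two recorded fields and pause dates; attendance already comes from the EMR. The ratio is less familiar than weeks. Like raw weeks, it has no value for participants who do not finish PR; percent completed covers them.
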